2.3 Exploratory and Correlative Objectives

2.3.1 Correlative Studies

The main objective of the translational research component of the IIT is to obtain biomarker measurements of PD-1 and PD-L1 expressions. Archival tumor samples will be sent to Qualtek Molecular Laboratories for analysis. See Sample Handling Manual.

2.4 Endpoints

Therapy administered until documented progression by RECIST 1.1 criteria or unacceptable toxicity.

This trial is a pilot study to assess the objective response rate with immunotherapy. There are no preliminary statistical assumptions. Stopping rules described in Section 9.

First response assessments at 9 weeks; time interval for trial assessment is typical for time interval for assessment of response to standard of care therapy. Investigational therapy will not preclude subsequent standard of care therapy or subsequent investigational therapy.

3.0 PATIENT ELIGIBILITY

3.1 Inclusion Criteria

- 3.1.1 Be willing and able to provide written informed consent/assent for the trial
- **3.1.2** Be ≥18 years of age on day of signing informed consent
- 3.1.3 Advanced BRCA-mutated and/or HDR-defect breast cancer progressing on or after prior therapy for metastatic disease or locally advanced disease; Prior therapy is defined as follows: for triple negative breast cancer progressing after at least 1 line of any prior chemotherapy; for HER2 positive disease must have progressed after at least two HER2 directed therapies in the metastatic setting including ado-trastuzumab emtansine (T-DM1); for hormone receptor positive disease (ER, PR, or both) must have progressed after a CDK4/CDK6 inhibitor plus hormonal therapy. Patients with progression within 12 months from previous neoadjuvant or adjuvant treatment could be enrolled in the study as 1st line therapy in metastatic setting.
- 3.1.4 Measurable disease by RECIST 1.1, with at least one lesion, not previously irradiated, that can be accurately measured at baseline as ≥ 10 mm in the longest diameter (except lymph nodes which must have short axis ≥ 15 mm) with computed tomography (CT) or magnetic resonance imaging (MRI) and which is suitable for accurate repeated measurements. Patients with non-measurable bone metastases in addition to measurable disease are eligible; however patients with non-measurable bone disease as the only site(s) of disease are not eligible.
- **3.1.5** ECOG 0 or 1
- **3.1.6** Documented BRCA deleterious germline or somatic mutation *AND/OR* HDR-defect.
- **3.1.7** FFPE tumor tissue available for analysis
- **3.1.8** Adequate organ function as defined in Table 1

Table 1 Adequate Organ Function Laboratory Values

System	Laboratory Value		
Hematological			
Absolute neutrophil count (ANC)	$\geq 1500/\mu L$		
Platelets	$\geq 100~000/\mu L$		
Hemoglobin	$\geq 10.0 \text{ g/dL or} \geq 5.6 \text{ mmol/L}^a$, with no blood		
	transfusion in the past 28 days		
Renal			
Creatinine OR	≤1.5 × ULN OR		
Measured or calculated ^b creatinine clearance	≥51 mL/min for participant with creatinine		
(GFR can also be used in place of creatinine or	levels >1.5 × institutional ULN		
CrCl)			
Hepatic			
Total bilirubin	≤1.5 ×ULN OR direct bilirubin ≤ULN for		
	participants with total bilirubin levels		
	>1.5 × ULN		

AST (SGOT) and ALT (SGPT)	≤2.5 × ULN (≤5 × ULN for participants with liver metastases)
Coagulation	
International normalized ratio (INR) OR prothrombin time (PT) Activated partial thromboplastin time (aPTT)	≤1.5 × ULN unless participant is receiving anticoagulant therapy as long as PT or aPTT is within therapeutic range of intended use of anticoagulants

ALT (SGPT)=alanine aminotransferase (serum glutamic pyruvic transaminase); AST (SGOT)=aspartate aminotransferase (serum glutamic oxaloacetic transaminase); GFR=glomerular filtration rate; ULN=upper limit of normal.

Note: This table includes eligibility-defining laboratory value requirements for treatment; laboratory value requirements should be adapted according to local regulations and guidelines for the administration of specific chemotherapies.

- **3.1.9** Female subjects: Postmenopausal or evidence of non-childbearing status for women of childbearing potential: negative urine or serum pregnancy test within 28 days of study treatment and confirmed prior to treatment on day 1.

 Postmenopausal is defined as:
 - Amenorrheic for 1 year or more following cessation of exogenous hormonal treatments Luteinizing hormone (LH) and Follicle stimulating hormone (FSH) levels in the post menopausal range for women under 50
 - radiation-induced oophorectomy with last menses >1 year ago
 - chemotherapy-induced menopause with >1 year interval since last menses
 - surgical sterilisation (bilateral oophorectomy or hysterectomy)

^a Criteria must be met without erythropoietin dependency and without packed red blood cell (pRBC) transfusion within last 2 weeks.

b Creatinine clearance (CrCl) should be calculated using Cockcroft-Gault equation or based on 24-hour urine.

Estimated creatinine clearance = (140-age [years]) x weight (kg) (x F)^a

serum creatinine (mg/dL) x 72

^a where F=0.85 for females and F=1 for males.

- 3.1.10 Women of childbearing potential and their partners, who are sexually active, must agree to the use of TWO highly effective forms of contraception in combination (as described in Appendix). This should be started from the signing of the informed consent and continue throughout the period of taking study treatment and for at least 1 month after last dose of study drug(s), or they must totally/truly abstain from any form of sexual intercourse (as described in Appendix).
- **3.1.11** Male patients must use a condom during treatment and for 3 months after the last dose of olaparib when having sexual intercourse with a pregnant woman or with a woman of childbearing potential. Female partners of male patients should also use a highly effective form of contraception ([see appendix for acceptable methods]) if they are of childbearing potential.
- **3.1.12** Patients must have a life expectancy ≥ 16 weeks

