3.2 Exclusion Criteria

- **3.2.1** Is currently participating or has participated in a study of investigational agent or using an investigational device with 30 days of the first dose of pembrolizumab.
- **3.2.2** a. Has had prior chemotherapy, targeted small molecule therapy, or radiation therapy within 3 weeks prior to study Day 1
 - b. Subjects must have recovered (i.e., \leq Grade 1 or at baseline) from any adverse events due to a previously administered agent. Subjects with \leq Grade 2 neuropathy are an exception to this criterion and may qualify for the study.
 - c. If subject received major surgery, they must have recovered adequately from the toxicity and/or complications from the intervention prior to starting therapy.
- **3.2.3** Is receiving systemic steroid therapy within three days prior to the first dose of pembrolizumab or receiving any other form of immunosuppressive medication
- **3.2.4** Is expected to require any other form of systemic or localized antineoplastic therapy while on trial.
 - Subjects with ER+/PR+ disease may be given endocrine therapy.
 - Subjects with HER2+ disease will be required to discontinue trastuzumab (Herceptin).
- **3.2.5** Has participated in another MK03475 trial.
 - **3.2.5.1** Note: Patients with or without prior PARP-inhibitor exposure may be included.
- 3.2.6 Concomitant use of known strong CYP3A inhibitors (eg. itraconazole, telithromycin, clarithromycin, protease inhibitors boosted with ritonavir or cobicistat, indinavir, saquinavir, nelfinavir, boceprevir, telaprevir) or moderate CYP3A inhibitors (eg. ciprofloxacin, erythromycin, diltiazem, fluconazole, verapamil). The required washout period prior to starting olaparib is 2 weeks.
- 3.2.7 Concomitant use of known strong (eg. phenobarbital, enzalutamide, phenytoin, rifampicin, rifabutin, rifapentine, carbamazepine, nevirapine and St John's Wort) or moderate CYP3A inducers (eg. bosentan, efavirenz, modafinil). The required washout period prior to starting olaparib is 5 weeks for enzalutamide or phenobarbital and 3 weeks for other agents.

- **3.2.8** Major surgery within 2 weeks of starting study treatment and patients must have recovered from any effects of any major surgery.
- **3.2.9** Has known hypersensitivity to pembrolizumab or any of its excipients

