4.2.3 Olaparib Management of Adverse Events

Management of haematological toxicity 4.2.3.1 Management of anaemia

Moderate CYP3A inhibitor

150 mg twice daily

Table 8	Management of anaemia							
Haemoglobin	Action to be taken							
Hb < 10 but ≥ 8 g/dl	First occurrence:							
(CTCAE Grade 2)	Give appropriate supportive treatment and investigate causality.							
	Investigator judgement to continue olaparib with supportive treatment (eg transfusion) or interrupt dose for a maximum of 4 weeks. Olaparib can be restarted if Hb has recovered to > 9g/dl.							
	Subsequent occurrences:							
	If Hb< 10 but ≥ 9 g/dI investigator judgement to continue olaparib with supportive treatment (eg transfusion) or dose interrupt (for max of 4 weeks) and upon recovery dose reduction may be considered (to 250 mg twice daily as a first step and to 200 mg twice daily as a second step).							
	If Hb< 9 but \geq 8 g/dI, dose interrupt (for max of 4 weeks) until Hb \geq 9 g/dI and upon recovery dose reduction may be considered (to 250 mg twice daily as a first step and to 200 mg twice daily as a second step).							
Hb < 8 g/dl (CTCAE Grade 3)	Give appropriate supportive treatment (e.g. transfusion) and investigate causality.							
,	Interrupt Olaparib for a maximum of 4 weeks until improved to Hb ≥ 9 g/dl.							
	Upon recovery dose reduce to 250 mg twice daily as a first step and to 200 mg twice daily as a second step in the case of repeat Hb decrease.							

Common treatable causes of anaemia (e.g., iron, vitamin B12 or folate deficiencies and hypothyroidism) should be investigated and appropriately managed. In some cases management of anaemia may require blood transfusions. For cases where patients develop prolonged haematological toxicity (≥2 week interruption/delay in olaparib due to CTC grade 3 or worse anaemia and/or development of blood transfusion dependence), refer to guidance later in this section for the management of this.

Management of neutropenia, leukopenia and thrombocytopenia

Table 9 Management of neutropenia, leukopenia and thrombocytopenia

Toxicity	Study treatment dose adjustment					
CTCAE Grade 1-2	Investigator judgement to continue treatment or if dose interruption, this should be for a maximum of 4 weeks; appropriate supportive treatment and causality investigation					

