10.3 Registration Procedures

All patients will be tracked following written informed consent. Those patients who are consented to participate in the clinical trial but do not meet one or more criteria required for participation during the screening phase will be listed as screen failures on the master list of consented subjects. Eligible subjects, as determined by screening procedures and verified by a treating investigator, will be registered on study at Cedars Sinai Medical Center by the Study Coordinator.

Issues that would cause treatment delays after registration should be discussed with the Principal Investigator (PI). If a patient does not receive protocol therapy following registration, the patient's registration on the study may be canceled. The Study Coordinator should be notified of cancellations as soon as possible.

Assignment of Subject ID: The study team will track all subjects who sign consent using OnCore. Subjects found to be ineligible will be recorded as screen failures. Subjects

found to be eligible will be registered using a three-digit numeric ID that follows the standard SOCCI format (001, 002, etc.).

A) Eligibility Verification

Prior to registration, all subjects must undergo eligibility verification by the SOCCI Cancer Clinical Trials Office (CCTO) Quality Management Core (QMC). The following documents will be organized into an eligibility packet, scanned as a pdf, and emailed to [contact] for review:

- QMC approved Eligibility Checklist signed by investigator and 2 members of the study team (or equivalent)
- Source documents substantiating eligibility that cannot be located in the subject's CS Link medical record
- Signed consent form with Subject's Bill of Rights, HIPAA authorization form, consent progress note, and any optional consent forms, as applicable, if not available in CS Link

B) Registration

After eligibility is verified, each site will assign the subject a study number and site staff will then register the patient in OnCore®.

Registration is completed as follows:

- Assign a patient study number
- Enter the patient in OnCore
- Notify the investigational pharmacy and treating physicians that a subject has gone on study and anticipated treatment start date

Oversight by the principal investigator is required throughout the entire registration process

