10.7.2 Protocol Exceptions and Eligibility Waivers

A protocol exception is an anticipated or planned deviation from the IRB-approved research protocol, as described in the IRB Policy, *Reporting Possible Unanticipated Problems Involving Risks to Subject or Others (UPIRSO) Policy: Institutional Review Board/Research Compliance and Quality Improvement.* A protocol exception most often involves a single subject and is not a permanent revision to the research protocol. Protocol exceptions that extend beyond a single subject should result in a protocol amendment to avoid serial violations.

Planned exceptions to the protocol that are more than logistical in nature and/or affect timing of study drug administration, or the investigator assesses the event may impact subject safety and/or study integrity, may not be implemented without prior approval from the SOCCI CCTO Medical Director and the IRB. The PI or her/his designee is responsible for submitting a protocol exception and its supporting documents to the SOCCI CCTO Medical Director for review and further instructions on IRB reporting.

Study team should refer to the IRB Reporting Possible Unanticipated Problems Involving Risks to Subject or Others (UPIRSO) Policy: Institutional Review Board/Research Compliance and Quality Improvement guidelines to determine which deviations and exception requests meet reporting guidelines. Once approved by the medical director, the deviation or exception request must be submitted to the IRB for review and approval prior to implementation.

Special considerations for Eligibility Waivers (EW)

Subjects who do not meet the eligibility requirements should not be enrolled. Eligibility waivers are not permitted.

Exception Request Submission Process

The PI and/or treating physician should provide a written request for a protocol exception including case history and justification for prospective deviation from the study design to the SOCCI CCTO Medical Director. The "IIT Exception Requests (ER) Form" must be completed then submitted, along with any applicable supporting documents, must be emailed to QMC ([contact]) to request a protocol exception from the CCTO Medical Director. This is only a requirement for studies with a DSM classification of moderate or high. An assessment from the CCTO Medical Director or designee must be done prior to submission to the IRB for review.

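### The haemoglobin entry limit in Table 1 is given as 10.0 g/dL or 5.6 mmol/L, which are two different values about 1 g/dL apart

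*Combined protocol and SAP*

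**What the plan says.** Section 3.1.8 requires adequate organ function as set out in Table 1. The haemoglobin row gives the limit in two units joined by a lower-case *or*: "\geq 10.0 \text{ g/dL or} \geq 5.6 \text{ mmol/L}^a". It also requires that no transfusion was given in the previous 28 days.

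The superscript points to footnote a, which begins "Criteria must be met without erythropoietin dependency" and then deals with transfusion. It says nothing about units. The note under the table gives these limits formal standing: "This table includes eligibility-defining laboratory value requirements for treatment". That note allows adaptation to local regulations and chemotherapy guidelines, which is a different matter from unit conversion.

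Four other places bear on the row:

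- Table 8 (Section 4.2.3.1) works in g/dL only. Its Grade 2 band is "Hb < 10 but ≥ 8 g/dl", and the first-occurrence rule begins "Investigator judgement to continue olaparib with supportive treatment".
- Exclusion 3.2.2b requires recovery to Grade 1 or baseline "from any adverse events due to a previously administered agent".
- Section 10.7.2 states "Eligibility waivers are not permitted".
- Section 10.3 requires a "QMC approved Eligibility Checklist signed by investigator" and study staff before registration.

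**The concern.** A limit quoted in two units should be one value written twice. Here the mmol/L figure corresponds to a clearly lower haemoglobin than the g/dL figure, so the row can be read in two ways:

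- **As literal alternatives.** Meeting either figure is enough. The lower one then always governs, the floor is about 9.0 g/dL, and the 10.0 g/dL limit does nothing.
- **As one limit in two units.** The row contradicts itself for any value between the two figures.

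Under the first reading, a patient could start treatment already inside Table 8's Grade 2 band, before any olaparib. Exclusion 3.2.2b narrows who that could be: Grade 2 anaemia caused by a previous agent is already excluded unless it is the patient's baseline. That leaves anaemia from other causes, such as the disease itself. Table 8 also lets olaparib continue in that band at the investigator's judgement. What is at stake is therefore an unclear entry limit; no safety hazard has been shown.

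**Working it through.** **Inputs.** From Table 1: 10.0 g/dL and 5.6 mmol/L. From outside the documents, as an assumption: haemoglobin monomer mass M = 16.114 g/mmol, varied below.

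**Formulas.** mmol/L = (g/dL × 10) / M, and g/dL = (mmol/L × M) / 10.

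**Can the plan's pair be reproduced?** No.

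- 10.0 g/dL: 100 / 16.114 = 6.206 mmol/L, against the stated 5.6.
- 5.6 mmol/L: 5.6 × 16.114 / 10 = 9.024 g/dL, against the stated 10.0.
- Gap: 10.0 − 9.024 = 0.976 g/dL, or 6.206 − 5.6 = 0.606 mmol/L.

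**Which reported values are caught?**

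| Hb (g/dL) | mmol/L | Meets 10.0 g/dL | Meets 5.6 mmol/L |
|---|---|---|---|
| 9.0 | 5.585 | no | only if rounded to 5.6 |
| 9.1 | 5.647 | no | yes |
| 9.5 | 5.895 | no | yes |
| 9.9 | 6.144 | no | yes |
| 10.0 | 6.206 | yes | yes |

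At one decimal, the nine values from 9.1 to 9.9 g/dL get opposite answers from the two figures.

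**Does the assumed mass matter?**

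| M (g/mmol) | 10.0 g/dL in mmol/L | 5.6 mmol/L in g/dL |
|---|---|---|
| 16.0 | 6.25 | 8.96 |
| 16.114 | 6.21 | 9.02 |
| 16.2 | 6.17 | 9.07 |
| 16.5 | 6.06 | 9.24 |

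The two figures agree only if M = 100 / 5.6 = 17.86 g/mmol, about 11% above the assumed value (17.86 / 16.114 = 1.108). Using the whole tetramer (64.458 g/mmol) does not help: 10.0 g/dL would then be 1.55 mmol/L.

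**Check of the corrected figure.** 6.2 mmol/L × 1.6114 = 9.99 g/dL, which is 10.0 at the precision used.

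**The case against.** The best counter-argument is that nobody would apply the mmol/L figure. Where Table 1 offers real alternatives (creatinine or clearance, total or direct bilirubin, INR or PT), it writes OR in capitals. The haemoglobin row has a lower-case *or* between two units of one analyte, so the natural reading is a 10.0 g/dL limit with a mis-stated equivalent. Table 8 is in g/dL with a boundary at 10, the creatinine formula uses mg/dL, and registration is at one named centre. A site reporting in g/dL would simply apply 10.0. On this view the error matters only if a laboratory reports in mmol/L, or someone converts a result, and the documents show neither.

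Much of this stands. The typography does favour the one-limit reading, and it is a good reason to keep 10.0 g/dL in the correction. It also supports expecting little practical effect. It does not make the row right: on the one-limit reading, the mmol/L figure is simply wrong.

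A second objection is that the ban on waivers does not stop staff interpreting an ambiguous criterion, and that the checklist may already carry a single value. That is fair, but the checklist is not part of the documents. A criterion that cannot be waived should give one answer without interpretation.

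A third is that the row has another loose end: the cell asks for 28 days without transfusion, and footnote a asks for 2 weeks. That is a separate inconsistency and does not affect the unit error.

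**Conclusion.** The concern holds. The two figures differ by 0.98 g/dL (0.61 mmol/L), and no text in the protocol reconciles them. The only outside assumption is the haemoglobin monomer mass. The mismatch persists for every value tried from 16.0 to 16.5 g/mmol; only the lower edge of the disputed band moves, from 8.96 to 9.24 g/dL.

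This is a drafting error in an eligibility-defining limit. It should be corrected, but it does not threaten the trial. The haemoglobin limit does not enter the error rate or power calculation in Section 9.2. How many patients fall in the disputed band cannot be worked out from the documents.

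**What to change.** In Table 1, change the mmol/L figure to 6.2 and put it in brackets in place of the *or*, so that the limit reads **≥ 10.0 g/dL (6.2 mmol/L)**. This keeps the unit used in the rest of the protocol and lines up with the upper edge of Table 8's Grade 2 band. If the sponsor did intend the lower floor, write **≥ 9.0 g/dL (5.6 mmol/L)** and drop 10.0. Carry the chosen value into the eligibility checklist required by Section 10.3.

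The cost is one table cell and one checklist line at the next amendment. With 10.0 g/dL kept, any patient at 9.1 to 9.9 g/dL would clearly not qualify. The 28-day and 2-week transfusion windows in the same row could be aligned in the same edit.

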- 3.2.22 Has an active autoimmune disease that has required systemic treatment in the past 2 years (i.e. with use of disease modifying agents, corticosteroids or immunosuppressive drugs). Subjects with vitiligo or resolved childhood asthma/atopy would be exception to this rule. Subjects that require inhaled steroid or local steroid injections will not be excluded from the study. Subjects with hypothyroidism not from autoimmune disease and stable on hormone replacement will not be excluded from the study. Note: Replacement therapy (eg., thyroxine, insulin, or physiologic

corticosteroid replacement therapy for adrenal or pituitary insufficiency, etc.) is not considered a form of systemic treatment.

- **3.2.23** Has had an allogenic tissue / solid organ transplant.
- **3.2.24** Previous allogenic bone marrow transplant or double umbilical cord blood transplantation (dUCBT).
- **3.2.25** Has a history or current evidence of any condition, therapy, or laboratory abnormality that might confound the results of the trial, interfere with the subject's participation for the full duration of the trial, or is not in the best interest of the subject to participate, in the opinion of the treating Investigator.
- **3.2.26** Has known psychiatric or substance abuse disorders that would interfere with cooperation with the requirements of the trial.
- 3.2.27 Is pregnant or breastfeeding, or expecting to conceive or father children within the projected duration of the trial, starting with the screening visit (Visit 1) through 120 days after the last dose of study treatment.

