If the toxicity does not resolve or the criteria for resuming treatment are not met, the participant must be discontinued from all study interventions.

If the toxicities do resolve and conditions are aligned with what is defined in Table 3, the combination of olaparib and pembrolizumab may be restarted at the discretion of the investigator. In these cases where the toxicity is attributed to the combination or to

olaparib alone, re-initiation of pembrolizumab as a monotherapy may be considered at the principal investigator's discretion.

Dosing Interruptions:

Dosing interruptions are permitted in the case of medical / surgical events or logistical reasons not related to study therapy (e.g., elective surgery, unrelated medical events, patient vacation, and/or holidays). Subjects should be placed back on study therapy within 3 weeks of the scheduled interruption, unless otherwise discussed with the Sponsor. The reason for interruption should be documented in the patient's study record.

Table 3: Dose Modification and Toxicity Management Guidelines for Immune-related AEs Associated with Pembrolizumab monotherapy and IO combinations

General instructions:

- 1. Severe and life-threatening irAEs should be treated with IV corticosteroids followed by oral steroids. Other immunosuppressive treatment should begin if the irAEs are not controlled by corticosteroids.
- 2. Study intervention must be permanently discontinued if the irAE does not resolve or the corticosteroid dose is not ≤10 mg/day within 12 weeks of the last study intervention treatment.
- 3. The corticosteroid taper should begin when the irAE is \leq Grade 1 and continue at least 4 weeks.
- 4. If study intervention has been withheld, study intervention may resume after the irAE decreased to ≤ Grade 1 after corticosteroid taper.

irAEs	Toxicity Grade (CTCAE v5.0)	Action With Pembrolizumab	Corticosteroid and/or Other Therapies	Monitoring and Follow-up
	Grade 2	Withhold	• Administer corticosteroids (initial dose of 1 to 2 mg/kg prednisone or equivalent)	Monitor participants for signs and symptoms of pneumonitis
Pneumonitis	Recurrent Grade 2, Grade 3 or 4	Permanently discontinue	 followed by taper Add prophylactic antibiotics for opportunistic infections 	Evaluate participants with suspected pneumonitis with radiographic imaging and initiate corticosteroid treatment

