5.15 Time and Events Table

	Screening				End of Treatment ⁴	SOC Follow- up ⁵								
Procedure	(Within 6 weeks of Day 1)	C1 D1	C1 D8	C1 D15	C2 D1	C2 D8	C3 D1	C4 D1	C5 D1	C6 D1	Even Cycles	Odd Cycles	30-days after drug discontinuation, +/- 7 days	Every 12 Weeks
Informed Consent ¹	Х													
Tempus HRD ¹¹	Х													
Physical Exam (includes Medical history)	х	х	х	х	х		х	х	х	х	X	×	Х	Х
Vitals ²	Х	Х	Х	Х	Х		Х	Х	Х	Х	Х	Х	Х	Х
ECOG Performance Status	х	х			Х		Х	Х	Х	Х	Х	Х	Х	Х
Hematology ⁸	Х	Х	Х	Х	Х	Х	Х	Х	Х	Х	Х	Х	Х	Х
Chemistry ⁸	Х	Х	Х	Х	Х	Х	Х	Х	Х	Х	Х	Х	Х	Х
Tumor markers (CA2729, CEA, CA- 125)		as per standard of care, at the investigator's discretion												
T3 Free, T4 Free, TSH ⁸	Х				Х			Х		Х	Х		Х	
Coagulation (PT, INR, aPTT)	X ⁸													
Urine or serum pregnancy test	X ₈													
EKG	Х													
Archival Tumor Tissue Collection	X ¹⁰													
CT Scan (Chest, Abdomen, Pelvis) and/or MRI	×		As clinically indicated (or every 9 weeks for Response assessment)						Х					
Whole body Bone Scan	Х		As clinically indicated											

Procedure	Screening (Within 6 weeks of Day 1)	Treatment Phase (+/- 3 days) ³											End of Treatment ⁴	SOC Follow- up ⁵
		C1 D1	C1 D8	C1 D15	C2 D1	C2 D8	C3 D1	C4 D1	C5 D1	C6 D1	Even Cycles	Odd Cycles	30-days after drug discontinuation, +/- 7 days	Every 12 Weeks
Adverse Event Assessment	Х		Х	Х	X		Х	Х	Х	Х	х	Х	Xe	X ⁶
Concomitant Medications	Х		Х	Х	X		Х	Х	Х	Х	Х	Х	Х	Х
Pembrolizu mab Administrati on		x			х		х	х	х	Х	Х	Х		
Olaparib Administrati on and Olaparib Compliance Diary			Daily ⁷											

¹Informed consent may be obtained within 6 weeks of Cycle 1, Day 1

²Vital signs to include temperature, pulse, respiratory rate, weight, and blood pressure. Height will be measured at Screening only.

³Study treatment is up to 35 administrations of pembrolizumab (approximately two years).

⁴If subject discontinues drug due to progression, the End of Treatment visit (30 days after study treatment discontinuation, +/- 7 days) will end their participation in the study and will not be followed thereafter.

⁵Subjects who discontinue trial treatment for a reason other than disease progression will move into the Follow-Up Phase and should be assessed every 12 weeks (56 ± 7 days) by radiologic imaging to monitor disease status, per standard of care for up to two years of total study participation.

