12.0 Appendix: Acceptable Birth Control Methods

Olaparib is regarded as a compound with medium/high foetal risk.

Women of childbearing potential and their partners, who are sexually active, must agree to the use of TWO highly effective forms of contraception in combination [as listed below]. This should be started from the signing of the informed consent and continue throughout the period of taking study treatment and for at least 1 month after last dose of study drug(s), or they must totally/truly abstain from any form of sexual intercourse (see below).

Male patients must use a condom during treatment and for 3 months after the last dose of olaparib when having sexual intercourse with a pregnant woman or with a woman of childbearing potential. Female partners of male patients should also use a highly effective form of contraception if they are of childbearing potential (as listed below). Male patients should not donate sperm throughout the period of taking olaparib and for 3 months following the last dose of olaparib.

Acceptable Non-hormonal birth control methods include:

Total/True abstinence: When the patient refrains from any form of sexual intercourse and this is in line with their usual and/or preferred lifestyle; this must continue for the total duration of the trial and for at least 1 month after the last dose of study drug <<for 3 months after last dose *for male patients*>>. [Periodic abstinence (e.g., calendar, ovulation, symptothermal, post-ovulation methods, or declaration of abstinence solely for the duration of a trial) and withdrawal are not acceptable methods of contraception]

Vasectomised sexual partner PLUS male condom. With participant assurance that partner received post-vasectomy confirmation of azoospermia.

Tubal occlusion PLUS male condom

IUD PLUS male condom. Provided coils are copper-banded

Acceptable hormonal methods:

Normal and low dose combined oral pills PLUS male condom

Cerazette (desogestrel) PLUS male condom. Cerazette is currently the only highly efficacious progesterone based pill.

Hormonal shot or injection (eg., Depo-Provera) PLUS male condom

Etonogestrel implants (e.g., Implanon, Norplant) PLUS male condom

Norelgestromin / EE transdermal system PLUS male condom

Intrauterine system [IUS] device (eg., levonorgestrel releasing IUS -Mirena®) PLUS male condom Intravaginal device (e.g., EE and etonogestrel) PLUS male condom

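### Post-treatment contraception periods (1 month for women, 3 months from olaparib for men) do not match the 120-day window in exclusion 3.2.27

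*Combined protocol and SAP*

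**What the plan says.** Four places set a reproductive window after treatment.

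- **Women, 3.1.10.** Women of childbearing potential who are sexually active use two highly effective methods from consent. They must "continue throughout the period of taking study treatment and for at least 1 month after last dose of study drug(s". True abstinence is the alternative. The Appendix (12.0) repeats the period: "for at least 1 month after last dose of study drug(s".
- **Men, 3.1.11.** "Male patients must use a condom during treatment and for 3 months after the last dose of olaparib", when the partner is pregnant or could become so. The Appendix repeats this and bars sperm donation while on olaparib and for 3 months after its last dose. For partners, 3.1.11 adds: "Female partners of male patients should also use a highly effective form of contraception". That sentence has no end date of its own.
- **Abstinence, Appendix.** It must last for the whole trial and for at least 1 month after the last study drug, or 3 months for men.
- **Exclusion 3.2.27.** Nobody enters who expects to conceive or father a child within the projected trial, a window running "starting with the screening visit (Visit 1) through 120 days after the last dose of study treatment".

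The two drugs need not stop together. Under 4.2.1, after a toxicity attributed to olaparib or to the combination, "re-initiation of pembrolizumab as a monotherapy may be considered". Sections 4.2.2 and 4.2.3 also call for stopping olaparib if 200 mg twice daily is not tolerated, if blood counts do not recover within 4 weeks of interruption, or if MDS or AML is confirmed. They recommend stopping it in severe renal impairment. None of these says that pembrolizumab must stop too.

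**The concern.** Section 3.2.27 asks about plans at entry. Contraception is what prevents an unplanned pregnancy. A participant with no such plans can satisfy 3.2.27, follow 3.1.10 or 3.1.11 to the letter, and still conceive or father a child within the 120 days that the protocol itself names.

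The men's clock is also tied to one drug of a two-drug regimen. If pembrolizumab goes on alone, the 3 months can be partly or wholly used up before the last study dose.

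Other provisions offer little backstop. For participants who stop for progression, the visit about 30 days after discontinuation "will end their participation in the study and will not be followed thereafter" (5.15, footnote 4). Pregnancy tests are scheduled only at screening and before the first dose. The pregnancy follow-up in 6.1.4 is worded for pregnancies that occur during pembrolizumab treatment.

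**Working it through.** The protocol gives no figure for these gaps, so there is none to reproduce. The check sets the stated periods against 120 days.

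**Inputs.** 1 month (3.1.10, Appendix); 3 months from olaparib (3.1.11, Appendix); 120 days from the last study treatment (3.2.27); End of Treatment visit at 30 ± 7 days (5.15). Depending on the start date, 1 calendar month is 28 to 31 days and 3 calendar months are 89 to 92 days.

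**Women using contraceptive methods.** Gap = 120 − (28 to 31):
- 120 − 31 = 89 days
- 120 − 28 = 92 days

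**Men, when both drugs stop together or olaparib stops last.** Gap = 120 − (89 to 92):
- 120 − 92 = 28 days
- 120 − 89 = 31 days

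**Men, when pembrolizumab outlasts olaparib.** Let m be the days from the last olaparib dose to the last pembrolizumab dose. Take 3 months as 90 days, and assume that condom use during treatment covers pembrolizumab as well. After the last pembrolizumab dose, max(0, 90 − m) days of required condom use remain, so gap = 120 − max(0, 90 − m).

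| m (days) | Condom days left | Gap (days) |
|---|---|---|
| 0 | 90 | 30 |
| 30 | 60 | 60 |
| 60 | 30 | 90 |
| 90 or more | 0 | 120 |

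Once m exceeds 90, the sperm-donation limit lapses while pembrolizumab dosing continues. With dosing every 3 weeks, this happens by the fifth further infusion if olaparib stops on an infusion day: 5 × 21 = 105 days.

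**Women relying on abstinence.** The answer depends on what the Appendix means by the duration of the trial.
- *The participant's own participation, stopping for progression.* Taking discontinuation as the last dose date, participation ends on day 30 − 7 = 23 to 30 + 7 = 37. Required abstinence ends at the later of that day and day 28 to 31, so between day 28 and day 37. Gap = 120 − 37 = 83 to 120 − 28 = 92 days.
- *Own participation, stopping for another reason.* Follow-up continues for up to two years of total participation, so there may be no gap.
- *The whole trial.* The Study Summary lists trial duration (42 months) separately from participation (2 to 24 months). On this reading the gap could be nil.

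**The case against.** The strongest reply is that the provisions differ in kind. Section 3.2.27 screens intent at entry, while 3.1.10, 3.1.11 and the Appendix govern conduct. All can be met at once, and 1 month is a minimum that forbids nothing longer. This stands. A reader might infer that 3.2.27 makes 120 days the protocol's contraception standard, so that the shorter periods contradict it. The text does not go that far.

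A reader might also take the Appendix's opening, "Olaparib is regarded as a compound with medium/high foetal risk", as support for 120 days. It is not. That statement introduces the 1- and 3-month periods, which are the Appendix's own response to that risk. No section gives a foetal-risk basis for 120 days for either drug.

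The Summary of Changes for version 6 records that olaparib template language was added to 3.1, 3.2 and the Appendix. It is tempting to conclude that the shorter periods were imported without being compared with 3.2.27. The log is compatible with that but does not show it.

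The consent form is not in the file, so the documents cannot show that participants were told only the shorter periods. That limits any claim about what participants know, but a consent form would not repair the rule written in the protocol.

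Finally, the protocol has real safeguards: two methods on treatment, pregnancy testing at entry, and removal from the study for pregnancy. The number of men, and of women of childbearing potential, among the 20 subjects is not given. These facts keep the point small. They do not align the periods.

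**Conclusion.** The mismatch is real and unreconciled. On minimum compliance, women using contraceptive methods may stop 89 to 92 days before day 120, and men may stop 28 to 31 days before it when both drugs stop together or olaparib stops last.

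The men's gap is larger whenever pembrolizumab outlasts olaparib, up to the full 120 days after the last pembrolizumab dose. Pembrolizumab restarted alone under 4.2.1 is not the only route. Discontinuation of olaparib under 4.2.2 or 4.2.3 has the same effect if pembrolizumab continues, which the text does not rule out. The up-to-120-day figure needs a male participant and at least 90 days of pembrolizumab after the last olaparib dose. The abstinence gap cannot be fixed without a definition of the trial's duration.

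Whether 120 days is the right period cannot be judged from these documents. What they support is that one consistent period is needed, counted from the right dose. This is a minor safety harmonisation. Endpoints, sample size, error rates and the stopping rule are untouched.

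**What to change.** 1. In 3.1.10, 3.1.11 and the Appendix, count the contraception, condom, sperm-donation, abstinence and female-partner periods from the last dose of either study drug, whichever is later.
2. Align those periods with the 120 days in 3.2.27, unless the Investigator's Brochure and package insert support a different period. In that case, use that one period in 3.1.10, 3.1.11, 3.2.27 and the Appendix.
3. Check that the consent form states the same period.
4. Give each participant the calendar end date at the End of Treatment visit, since those who progress leave the study then.

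The cost is a few lines of wording, a check of the consent form and one instruction at an existing visit. If 120 days is kept, the burden on participants is about 3 more months of contraception for women using contraceptive methods (89 to 92 days). For men it is about 1 more month (28 to 31 days) when both drugs stop together, and longer when pembrolizumab outlasts olaparib.
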